9.8 Safety Evaluations	Vital signs description added to specify pulse/heart rate and blood pressure evaluation methods and timings, ie, at every protocol-specified visit until end of treatment
------------------------	---

Rationale: To add an external link for examples of CYP3A inhibitors and inducers; to add additional dose reduction information for CYP3A co-administration

Attachment 4 Instruction for Concomitant Medications to be Used With Precaution, Attachment 5 Inhibitors and Inducers of CYP3A	Inserted an additional link to FDA classification of CYP3A inhibitors and inducers in Attachment 4 and Attachment 5 Updated dose reduction description in Attachment 4
--	---

Attachment 1 Ibrutinib Dosing Guides, Attachment 2 Potential Dose for Younger Subjects	Added dosing tables for 330 mg/m ² , 220 mg/m ² , and 110 mg/m ² (ie, dose reductions in patients starting at 440 mg/m ²) Moved dosing table for 440 mg/m ² to Attachment 1; Attachment 2 deleted
--	--

Rationale: To improve clarity and accuracy throughout the protocol

Table 1 and Table 2 Time and Events Schedules	Added a separate Time and Events Schedule for Part 2 of the study (Table 2); removed references to Part 2 as appropriate
---	--

Table 1, Table 3, Table 4, Table 5 Time and Events Schedules, Attachment 7 Blood Volume Tables	Added and/or edited headings and footnotes for clarity
3.1 Overview of Study Design	Clarified pharmacokinetic sampling to be obtained only for subjects receiving ibrutinib in combination with background therapy in Part 2
3.1 Overview of Study Design, 6.1 Study Treatment, 9.1.4 Posttreatment Phase (Follow-up)	Clarified subjects must have completed 3 cycles of treatment to be eligible to receive ibrutinib monotherapy
Figure 2 Schematic Overview of the Study (Part 2; Randomized Part), 4.1 Inclusion Criteria	Eligibility criteria updated to specify subjects were to have received only 1 prior line of therapy for inclusion in Part 2 of the study
6 Dosage and Administration	Added reference to Investigational Product Preparation Instruction for subjects requiring dosing through a feeding tube
6.1.2 Ibrutinib Administration	Clarified methods for dispensing ibrutinib by cycle
9.2.3 Lumbar Puncture	Provided additional information for lumbar puncture and cerebral spinal fluid collection
Table 9 International Pediatric non-Hodgkin lymphomas (NHL) Response Criteria	Updated to align with guidance

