6.2.2. Ibrutinib

Treatment with ibrutinib should be temporarily stopped for any unmanageable, potentially study drug-related toxicity that is Grade \geq 3 in severity. Hematologic toxicities are expected with RICE and RVICI and it may not be feasible to determine any relationship to ibrutinib. If the hematologic toxicities are not manageable, ibrutinib should be temporarily stopped, however, if

the cytopenias can be managed with transfusion and/or growth factor support and there are no unmanageable secondary complications from these cytopenias (eg, serious infection, significant bleeding) ibrutinib may be continued, at the discretion of the investigator. Ibrutinib may be temporarily stopped for a maximum of 21 consecutive days unless reviewed and approved by the sponsor. Ibrutinib should be discontinued permanently in the event of a toxicity lasting more than 21 days. If ibrutinib is delayed or temporarily stopped, any remaining study treatment (ie, rituximab, ifosfamide, carboplatin, etoposide, vincristine, idarubicin, and dexamethasone) may be continued.

The actions in [Table 8](#) below should be taken for the following drug-related toxicities. Changes must be recorded in the Drug Accountability Records and Dosage Administration page of the electronic CRF.

- Grade 3 or greater febrile neutropenia
- Grade 4 neutropenia (ANC $<0.5 \times 10^9/L$ [ie, $<500/\text{mm}^3$]) for >14 days (after completion of CIT)
- Grade 3 thrombocytopenia (platelets $<50 \times 10^9/L$ [ie, $<50,000/\text{mm}^3$]) in the presence of significant bleeding (ie, \geq Grade 2 bleeding)
- Grade 4 thrombocytopenia (platelets $<25 \times 10^9/L$ [ie, $<25,000/\text{mm}^3$])
- Grade 3 or greater non-hematological toxicity

Table 8: Ibrutinib Dose Modifications

Occurrence of the Same Adverse Event	Action
First	Temporarily stop study drug until recovery to Grade ≤ 1 or baseline; may restart at original dose level
Second	Temporarily stop study drug until recovery to Grade ≤ 1 or baseline; restart at 25% decrease in dose (ie, 1 dose level lower) ^a
Third	Temporarily stop study drug until recovery to Grade ≤ 1 or baseline; restart at 50% decrease in dose (ie, 1 dose level lower) ^a
Fourth	Discontinue study drug

a. Consult the sponsor for calculation of the reduced dose to be administered, if needed.

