Refer to [Attachment 1](#) for BSA-based dosing/rounding. Refer to [Attachment 4](#) for instructions on dose modifications or temporary stop during concomitant administration of CYP3A inhibitors or inducers for subjects taking ibrutinib. Refer to Section [4.3](#) for guidance on dose delays during the perioperative period for subjects who require surgical intervention or an invasive procedure while receiving study drug.

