Attachment 1: Ibrutinib Dosing Guides**Suspension and Capsule Dosing 329 mg/m²
(Full Dose Equivalent; 560 mg/1.7 m²)**

Body Surface Area (m ²)		Target Dose (mg)	Suspension (70 mg/mL) Volume to be Administered (mL)	Actual Dose to Administer by Suspension (mg)	# 70 mg Capsules ^{a,b}	Actual Dose to Administer by Capsule (mg)
From	To					
0.30	0.34	98.8	1.4	98	-	-
0.35	0.39	115.3	1.6	112	-	-
0.40	0.44	131.8	1.9	133	-	-
0.45	0.49	148.2	2.1	147	-	-
0.50	0.54	164.7	2.4	168	-	-
0.55	0.59	181.2	2.6	182	-	-
0.60	0.64	197.6	2.8	196	3	210
0.65	0.69	214.1	3.1	217	3	210
0.70	0.74	230.6	3.3	231	3	210
0.75	0.79	247.1	3.5	245	4	280
0.80	0.84	263.5	3.8	266	4	280
0.85	0.89	280.0	4.0	280	4	280
0.90	0.94	296.5	4.2	294	4	280
0.95	0.99	312.9	4.5	315	4	280
1.00	1.04	329.4	4.7	329	5	350
1.05	1.09	345.9	4.9	343	5	350
1.10	1.14	362.4	5.2	364	5	350
1.15	1.19	378.8	5.4	378	5	350
1.20	1.24	395.3	5.6	392	6	420
1.25	1.29	411.8	5.9	413	6	420
1.30	1.34	428.2	6.1	427	6	420
1.35	1.39	444.7	6.4	448	6	420
1.40	1.44	461.2	6.6	462	7	490
1.45	1.49	477.6	6.8	476	7	490
1.50	1.54	494.1	7.1	497	7	490
1.55	1.59	510.6	7.3	511	7	490
1.60	1.64	527.1	7.5	525	8	560
1.65	1.69	543.5	7.8	546	8	560
1.70 and higher		560.0	8.0	560	8	560

a. Rounded to nearest 70 mg capsule.

b. For older children, one 140-mg capsule may be substituted for each two 70-mg capsules.

**Suspension and Capsule Dosing for the 240 mg/m² Dose
(Full Dose Equivalent; 420 mg/1.7 m²)**

Body Surface Area (m ²)		Target Dose (mg)	Suspension (70 mg/mL) Volume to be Administered (mL)	Actual Dose to Administer by Suspension (mg)	# 70 mg Capsules ^{a,b}	Actual Dose to Administer by Capsule (mg)
From	To					
0.30	0.34	72.0	1.0	70	-	-
0.35	0.39	84.0	1.2	84	-	-
0.40	0.44	96.0	1.4	98	-	-
0.45	0.49	108.0	1.5	105	-	-
0.50	0.54	120.0	1.7	119	-	-
0.55	0.59	132.0	1.9	133	-	-
0.60	0.64	144.0	2.1	147	2	140
0.65	0.69	156.0	2.2	154	2	140
0.70	0.74	168.0	2.4	168	2	140
0.75	0.79	180.0	2.6	182	3	210
0.80	0.84	192.0	2.7	189	3	210
0.85	0.89	204.0	2.9	203	3	210
0.90	0.94	216.0	3.1	217	3	210
0.95	0.99	228.0	3.3	231	3	210
1.00	1.04	240.0	3.4	238	3	210
1.05	1.09	252.0	3.6	252	4	280
1.10	1.14	264.0	3.8	266	4	280
1.15	1.19	276.0	3.9	273	4	280
1.20	1.24	288.0	4.1	287	4	280
1.25	1.29	300.0	4.3	301	4	280
1.30	1.34	312.0	4.5	315	4	280
1.35	1.39	324.0	4.6	322	5	350
1.40	1.44	336.0	4.8	336	5	350
1.45	1.49	348.0	5.0	350	5	350
1.50	1.54	360.0	5.1	357	5	350
1.55	1.59	372.0	5.3	371	5	350
1.60	1.64	384.0	5.5	385	5	350
1.65	1.69	396.0	5.7	399	6	420
1.70	1.74	408.0	5.8	406	6	420

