1.60	1.64	192.0	2.7	189	3	210
1.65	1.69	198.0	2.8	196	3	210
1.70	1.74	204.0	2.9	203	3	210
1.75 or higher		210.0	3.0	210	3	210

a. Rounded to nearest 70 mg capsule.

b. For older children, one 140-mg capsule may be substituted for each two 70-mg capsules.

Suspension and Capsule Dosing 80 mg/m²
(Full Dose Equivalent; 140 mg/1.7 m²)

Body Surface Area (m ²)		Target Dose (mg)	Suspension (70 mg/mL) Volume to be Administered (mL)	Actual Dose to Administer by Suspension (mg)	# 70 mg Capsules ^{a,b}	Actual Dose to Administer by Capsule (mg)
From	To					
0.30	0.34	24.0	0.3	21	-	-
0.35	0.39	28.0	0.4	28	-	-
0.40	0.44	32.0	0.5	35	-	-
0.45	0.49	36.0	0.5	35	-	-
0.50	0.54	40.0	0.6	42	-	-
0.55	0.59	44.0	0.6	42	-	-
0.60	0.64	48.0	0.7	49	-	-
0.65	0.69	52.0	0.7	49	-	-
0.70	0.74	56.0	0.8	56	-	-
0.75	0.79	60.0	0.9	63	-	-
0.80	0.84	64.0	0.9	63	-	-
0.85	0.89	68.0	1.0	70	-	-
0.90	0.94	72.0	1.0	70	-	-
0.95	0.99	76.0	1.1	77	-	-
1.00	1.04	80.0	1.1	77	-	-
1.05	1.09	84.0	1.2	84	-	-
1.10	1.14	88.0	1.3	91	-	-
1.15	1.19	92.0	1.3	91	-	-
1.20	1.24	96.0	1.4	98	-	-
1.25	1.29	100.0	1.4	98	-	-
1.30	1.34	104.0	1.5	105	-	-
1.35	1.39	108.0	1.5	105	-	-
1.40	1.44	112.0	1.6	112	2	140
1.45	1.49	116.0	1.7	119	2	140
1.50	1.54	120.0	1.7	119	2	140
1.55	1.59	124.0	1.8	126	2	140
1.60	1.64	128.0	1.8	126	2	140
1.65	1.69	132.0	1.9	133	2	140
1.70	1.74	136.0	1.9	133	2	140
1.75 and higher		140.0	2.0	140	2	140

a. Rounded to nearest 70 mg capsule.

b. For older children, one 140-mg capsule may be substituted for each two 70-mg capsules.

**Suspension and Capsule Ibrutinib Dosing 440 mg/m²
(Full Dose Equivalent; 748 mg/1.7 m²)**

**NOTE: only to be used in subjects under 12 years of age-dose administered will not exceed
560 mg**

Body Surface Area (m ²)		Target Dose (mg)	Suspension (70 mg/mL) Volume to be Administered (mL)	Actual Dose to Administer by Suspension (mg)	# 70 mg Capsules ^{a,b}	Actual Dose to Administer by Capsule (mg)
From	To					
0.30	0.34	132	1.9	133	-	-
0.35	0.39	154	2.2	154	-	-
0.40	0.44	176	2.5	175	-	-
0.45	0.49	198	2.8	196	-	-
0.50	0.54	220	3.1	217	-	-
0.55	0.59	242	3.5	245	3	210
0.60	0.64	264	3.8	266	4	280
0.65	0.69	286	4.1	287	4	280
0.70	0.74	308	4.4	308	4	280
0.75	0.79	330	4.7	329	5	350
0.80	0.84	352	5.0	350	5	350
0.85	0.89	374	5.3	371	5	350
0.90	0.94	396	5.7	399	6	420
0.95	0.99	418	6.0	420	6	420
1.00	1.04	440	6.3	441	6	420
1.05	1.09	462	6.6	462	7	490
1.10	1.14	484	6.9	483	7	490
1.15	1.19	506	7.2	504	7	490
1.20	1.24	528	7.5	525	8	560
1.25	1.29	550	7.9	553	8	560
1.30	1.34	560	8.0	560	8	560

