1.35	1.39	560	8.0	560	8	560
1.40	1.44	560	8.0	560	8	560
1.45	1.49	560	8.0	560	8	560
1.50	1.54	560	8.0	560	8	560
1.55	1.59	560	8.0	560	8	560
1.60	1.64	560	8.0	560	8	560
1.65	1.69	560	8.0	560	8	560
1.70 and higher		560	8.0	560	8	560

a. Rounded to nearest 70 mg capsule.

b. For older children, one 140-mg capsule may be substituted for each two 70-mg capsules.

Suspension and Capsule Dosing 330 mg/m²
(Full Dose Equivalent; 561 mg/1.7 m²)

Body Surface Area (m ²)	Target Dose (mg)	Suspension (70 mg/mL) Volume to be Administered (mL)	Actual Dose to Administer by Suspension (mg)	# 70 mg Capsules ^{a,b}	Actual Dose to Administer by Capsule (mg)
From	To				
0.30	0.34	99.0	1.4	98	-
0.35	0.39	115.5	1.7	119	-
0.40	0.44	132.0	1.9	133	-
0.45	0.49	148.5	2.1	147	-
0.50	0.54	165.0	2.4	168	-
0.55	0.59	181.5	2.6	182	-
0.60	0.64	198.0	2.8	196	3
0.65	0.69	214.5	3.1	217	3
0.70	0.74	231.0	3.3	231	3
0.75	0.79	247.5	3.5	245	3
0.80	0.84	264.0	3.8	266	4
0.85	0.89	280.5	4.0	280	4
0.90	0.94	297.0	4.2	294	4
0.95	0.99	313.5	4.5	315	4
1.00	1.04	330.0	4.7	329	5
1.05	1.09	346.5	5.0	350	5
1.10	1.14	363.0	5.2	364	5
1.15	1.19	379.5	5.4	378	5
1.20	1.24	396.0	5.7	399	6
1.25	1.29	412.5	5.9	413	6
1.30	1.34	429.0	6.1	427	6
1.35	1.39	445.5	6.4	448	6
1.40	1.44	462.0	6.6	462	7
1.45	1.49	478.5	6.8	476	7
1.50	1.54	495.0	7.1	497	7
1.55	1.59	511.5	7.3	511	7
1.60	1.64	528.0	7.5	525	8
1.65	1.69	544.5	7.8	546	8
1.70 and higher	560.0	8.0	560	8	560

a. Rounded to nearest 70 mg capsule.

b. For older children, one 140-mg capsule may be substituted for each two 70-mg capsules.

Suspension and Capsule Dosing 220 mg/m²
(Full Dose Equivalent; 374 mg/1.7 m²)

Body Surface Area (m ²)	Target Dose (mg)	Suspension (70 mg/mL) Volume to be Administered (mL)	Actual Dose to Administer by Suspension (mg)	# 70 mg Capsules ^{a,b}	Actual Dose to Administer by Capsule (mg)
From	To				
0.30	0.34	66.0	0.9	63	-
0.35	0.39	77.0	1.1	77	-
0.40	0.44	88.0	1.3	91	-
0.45	0.49	99.0	1.4	98	-
0.50	0.54	110.0	1.6	112	-
0.55	0.59	121.0	1.7	119	-
0.60	0.64	132.0	1.9	133	2
0.65	0.69	143.0	2.0	140	2
0.70	0.74	154.0	2.2	154	2
0.75	0.79	165.0	2.4	168	2
0.80	0.84	176.0	2.5	175	3
0.85	0.89	187.0	2.7	189	3
0.90	0.94	198.0	2.8	196	3
0.95	0.99	209.0	3.0	210	3
1.00	1.04	220.0	3.1	217	3
1.05	1.09	231.0	3.3	231	3
1.10	1.14	242.0	3.5	245	3
1.15	1.19	253.0	3.6	252	4
1.20	1.24	264.0	3.8	266	4
1.25	1.29	275.0	3.9	273	4
1.30	1.34	286.0	4.1	287	4
1.35	1.39	297.0	4.2	294	4
1.40	1.44	308.0	4.4	308	4
1.45	1.49	319.0	4.6	322	5
1.50	1.54	330.0	4.7	329	5

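### The 330 mg/m² dose-reduction table lists 3 capsules for BSA 0.75–0.79 m² where its rounding rule gives 4, turning a 25% reduction into a 40% one

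*Protocol*

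**What the plan says.** - **Rounding rule.** Footnote a of each table in Protocol Attachment 1 reads "Rounded to nearest 70 mg capsule".
- **The row in question.** In the 330 mg/m² table, the BSA 0.75–0.79 m² row reads "0.75 0.79 247.5 3.5 245 3": a target of 247.5 mg, 3.5 mL of suspension (245 mg), and 3 capsules.
- **Same band, 329 mg/m² table.** The row reads "0.75 0.79 247.1 3.5 245 4 280": a target of 247.1 mg, the same suspension dose, but 4 capsules (280 mg).
- **Same band, 440 mg/m² table.** The row reads "0.75 0.79 330 4.7 329 5 350": 5 capsules (350 mg). This dose is "only to be used in subjects under 12 years of age".
- **Use of the 330 mg/m² table.** The Amendment 5 change log says the 330, 220 and 110 mg/m² tables were added for "dose reductions in patients starting at 440" mg/m².
- **Size of the reduction.** Section 6.2.2, Table 8, at the second occurrence of the same adverse event: "restart at 25% decrease in dose (ie, 1 dose level lower"). The same section sends sites to Attachment 1 "for BSA-based dosing/rounding".

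**The concern.** Under one rounding rule a higher target cannot need fewer capsules, yet 247.5 mg is given 3 and 247.1 mg is given 4. One of the two rows must be wrong, and the footnote points to the 330 mg/m² row.

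This is an operative dosing figure for children, used when a toxicity has recurred and the dose has to be stepped down by a set amount. An overlarge step leaves the child below the intended dose. Exposure matters in this age range: the Amendment 3 log records lower than expected ibrutinib exposure in the two younger age groups, and a 440 mg/m² table was added as a higher option in case exposure stayed too low.

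**Working it through.** **Inputs.** Capsule strength 70 mg and nearest-capsule rounding (Attachment 1, footnote a). Targets and counts from the 440, 330, 329 and 160 mg/m² tables. Prescribed first reduction 25% (Table 8); 440 × 0.75 = 330 mg/m², so the 330 table is that step.

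**1. Capsule count.** Formula: capsules = target ÷ 70, rounded to the nearest whole number.

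| Table | BSA band (m²) | Target (mg) | Target ÷ 70 | Rounds to | Listed |
|---|---|---|---|---|---|
| 330 mg/m² | 0.75–0.79 | 247.5 | 3.536 | 4 | **3** |
| 329 mg/m² | 0.75–0.79 | 247.1 | 3.530 | 4 | 4 |
| 160 mg/m² | 1.55–1.59 | 248.0 | 3.543 | 4 | 4 |

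The listed targets use the lower limit of the band (330 × 0.75 = 247.5). Mid-band (330 × 0.77 = 254.1; ÷ 70 = 3.63) and top of band (330 × 0.79 = 260.7; ÷ 70 = 3.72) also round to 4.

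**2. Could another rule give 3?**
- Rounding down gives 3 here but fails in the same table: 198 mg (2.83) is listed as 3 and 264 mg (3.77) as 4.
- Rounding the 245 mg suspension dose (3.5) half-down gives 3, but the 329 mg/m² table lists 4 for the same 245 mg, and the 220 mg/m² table lists 6 for 385 mg (5.5).
- Nearest-capsule rounding of the target reproduces every other capsule count in all nine tables. This row is the only mismatch.

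**3. Effect on the first reduction.** Formula: cut = 1 − (dose at 330 mg/m²) ÷ (dose at 440 mg/m²).
- As listed: 1 − 210/350 = 40%.
- With 4 capsules: 1 − 280/350 = 20%.
- Suspension, same band: 1 − 245/329 = 25.5%, so suspension users are unaffected.

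**4. Comparison with the other bands.** Capsule counts from 440 to 330 mg/m², for the bands where the 440 mg/m² dose is not capped at 560 mg:

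| BSA bands (m²) | Capsules | Cut |
|---|---|---|
| 0.60–0.74 (three bands) | 4 → 3 | 25% |
| **0.75–0.79** | **5 → 3** | **40%** |
| 0.80–0.89 (two bands) | 5 → 4 | 20% |
| 0.90–0.99 (two bands) | 6 → 4 | 33% |
| 1.00–1.04 | 6 → 5 | 17% |
| 1.05–1.19 (three bands) | 7 → 5 | 29% |
| 1.20–1.29 (two bands) | 8 → 6 | 25% |

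The 13 other bands lie between 17% and 33%. Above 1.29 m² the 560 mg cap makes the cut smaller or leaves it at 25%, down to 0% from 1.60 m².

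**5. Deviation from the row's own target.** 210/247.5 = 0.848 (−15%) as listed; 280/247.5 = 1.131 (+13%) if corrected.

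**The case against.** The rounding error itself is hard to dispute. The stronger objections concern evidence, framing and weight.

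- **One digit in a damaged table.** The capsule-mg column of the 330 mg/m² table is missing from the available text, so 210 mg is inferred. If the PDF prints 280 mg beside the 3, the row is inconsistent with itself and not plainly an underdose. This stands as a reason to check the PDF first. A column shift is unlikely: the last row is complete and fixes the column order, and every other count agrees with target ÷ 70.
- **The 40% combines two roundings.** Part of it comes from the 440 mg/m² table correctly rounding 330 mg up to 350 mg. Against the nominal 330 mg the listed dose is a 36% cut (1 − 210/330). The two capsule choices are also nearly equidistant from the target (37.5 mg below, 32.5 mg above). All true, but 40% is the change in the dose the child actually takes, and only 4 follows the stated rule.
- **Rows that obey the rule deviate by more than 15%.** In the 110 mg/m² table, 104.5 mg becomes 70 mg (−33%); in the 80 mg/m² table, 112 mg becomes 140 mg (+25%). Correct, but that is the unavoidable coarseness of 70 mg capsules. Here the extra deviation is avoidable.
- **Reach may be nil.** It takes a child under 12 on 440 mg/m², in this band, on capsules, with a second occurrence of the same toxicity. Nothing in the documents shows that anyone received 440 mg/m², and enrollment has stopped. This limits the importance. Section 17.9.1 does let ongoing patients continue treatment, and past doses may have come from this row.
- **Sponsor consultation.** Table 8 allows it where the reduced dose needs calculating. A site with a printed row has no evident reason to ask.
- **No endpoint or analysis is affected, and the error lowers the dose in a child with recurrent toxicity.** Also true. It keeps the point modest but does not make the figure right.

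**Conclusion.** The concern holds. The 330 mg/m² row for BSA 0.75–0.79 m² should list 4 capsules (280 mg). As listed, the first capsule reduction from 440 mg/m² is 40%, which is 15 percentage points beyond the prescribed 25% and outside the 17–33% seen in the other uncapped bands. Corrected, it is 20%, 5 points short of the prescribed figure and as close as whole capsules allow.

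This rests on two assumptions: that the 3 is what the PDF prints, and that 3 capsules means 3 × 70 = 210 mg. The consequence is confined to capsule users in one BSA band at one reduction step.

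**What to change.** 1. Check the capsule count and the capsule-mg entry for this row against the PDF.
2. Change the row to 4 capsules (280 mg).
3. Notify sites and pharmacies, and correct any copy of the table in the pharmacy manual.
4. Check dosing records for capsule users reduced from 440 mg/m² in this BSA band.

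The cost is one table row, one notification and a short record check. No analysis, sample size or endpoint changes.

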Attachment 2: Lansky-Karnofsky Performance Status

Karnofsky Scale^a (recipient age ≥ 16 years)	Lansky Scale^b (recipient age < 16 years)
100: Normal, no complaints, no evidence of disease	100: Fully active, normal
90: Able to carry on normal activity. Minor signs or symptoms of disease.	90: Minor restriction with strenuous physical activity
80: Normal activity with effort. Some signs or symptoms of disease.	80: Active, but gets tired more quickly
70: Cares for self, unable to carry on normal activity or to do active work	70: Both greater restrictions of, and less time spent in, active play
60: Requires occasional assistance but is able to care for most of personal needs	60: Up and around, but minimal active play; keeps busy with quieter activities
50: Requires considerable assistance and frequent medical care	50: Lying around much of the day, but gets dressed; no active play; participates in all quiet play and activities
40: Disabled, requires special care and assistance	40: Mostly in bed; participates in quiet activities
30: Severely disabled, hospitalization indicated, although death not imminent	30: Stuck in bed; needs help even for quiet play
20: Hospitalization necessary. Very sick, active supportive treatment necessary.	20: Often sleeping; play is entirely limited to very passive activities
10: Moribund, fatal process progressing rapidly	10: Does not play or get out of bed to play
0: Dead	0: Unresponsive

a. Karnofsky DA, Burchenal JH. The clinical evaluation of chemotherapeutic agents in cancer. In Evaluation of chemotherapeutic agents. Edited by MacLeod CM. New York: Columbia University Press; 1949:191-205.¹⁷

b. Lansky SB, List MA, Lansky LL, Ritter-Stern C, Miller DR. The measurement of performance in childhood cancer patients. *Cancer*. 1987 Oct 1;60(7):1651-1656.²⁰

Attachment 3: Body Surface Area Calculation

BSA should be calculated using a standard nomogram. An example nomogram follows:

$$\text{BSA} = \sqrt{\frac{Ht(\text{inches}) \times Wt(\text{lbs})}{3131}}$$

or

$$\text{BSA} = \sqrt{\frac{Ht(\text{cm}) \times Wt(\text{kg})}{3600}}$$

Attachment 4: Instruction for Concomitant Medications to be Used With Precaution

Ibrutinib is metabolized primarily by CYP3A. Avoid co-administration with strong or moderate CYP3A inhibitors and consider alternative agents with less CYP3A inhibition. Co-administration of ketoconazole, a strong CYP3A inhibitor, in 18 healthy subjects increased dose normalized exposure, C_{max} and AUC₀-last, of ibrutinib by 29- and 24-fold, respectively. A DDI study in patients with B-cell malignancies (PCI-32765LYM1003) found that co-administration of ibrutinib with the moderate CYP3A inhibitors erythromycin and voriconazole, increased C_{max} by 3.4-fold and 6.7-fold and increased AUC by 3.0-fold and 5.7-fold, respectively. Clinical safety data in 66 subjects treated with moderate (n=47) or strong CYP3A inhibitors (n=19) did not reveal meaningful increases in toxicities. Strong inhibitors of CYP3A (eg, ketoconazole, indinavir, nelfinavir, ritonavir, saquinavir, clarithromycin, telithromycin, itraconazole, nefazadone, and cobicistat) and moderate inhibitors (eg, voriconazole, erythromycin, amprenavir, aprepitant, atazanavir, ciprofloxacin, crizotinib, darunavir/ritonavir, diltiazem, fluconazole, fosamprenavir, imatinib, verapamil, amiodarone, dronedarone) should be avoided. If the benefit outweighs the risk and a strong CYP3A inhibitor must be used, reduce the ibrutinib dose by 75% (140 mg/1.7 m² rounded down to 80 mg/m² for starting dose of 329 mg/m² or to 110 mg/m² for dose of 440 mg/m²) or stop treatment temporarily (for 7 days or less). If a moderate CYP3A inhibitor must be used, reduce ibrutinib by 75% (140 mg/1.7 m² rounded down to 80 mg/m² for starting dose of 329 mg/m² or to 110 mg/m² for dose of 440 mg/m²) for the duration of the inhibitor use. No dose adjustment is required in combination with mild inhibitors. Monitor the subject closely for toxicity and follow dose modification guidance as needed. Avoid grapefruit and Seville oranges during ibrutinib treatment, as these contain moderate inhibitors of CYP3A.

Co-administration of ibrutinib with strong inducers of CYP3A decreases ibrutinib plasma concentrations by up to 90%. Avoid concomitant use of strong CYP3A inducers (eg, carbamazepine, rifampin, phenytoin, and St. John's Wort). Consider alternative agents with less CYP3A induction.

Examples of inhibitors, inducers, and substrates can be found in [Attachment 5](#) and at <https://www.fda.gov/drugs/drug-interactions-labeling/drug-development-and-drug-interactions-table-substrates-inhibitors-and-inducers>¹¹ and <http://medicine.iupui.edu/clinpharm/ddis/main-table/>.¹⁰

Drugs That May Have Their Plasma Concentrations Altered by Ibrutinib

In vitro studies indicated that ibrutinib is a weak reversible inhibitor toward CYP2B6, CYP2C8, CYP2C9, CYP2C19, CYP2D6, and CYP3A4/5 and does not display time-dependent CYP450 inhibition. The dihydrodiol metabolite of ibrutinib is a weak inhibitor toward CYP2B6, CYP2C8, CYP2C9, and CYP2D6. Both ibrutinib and the dihydrodiol metabolite are at most weak inducers of CYP450 isoenzymes in vitro. Therefore, it is unlikely that ibrutinib has any clinically relevant drug-drug interactions with drugs that may be metabolized by the CYP450 enzymes.

In vitro studies indicated that ibrutinib is not a substrate of P-glycoprotein (P-gp) nor other major transporters, except OCT2. The dihydrodiol metabolite and other metabolites are P-gp substrates. Ibrutinib is a mild inhibitor of P-gp and breast cancer resistance protein (BCRP). Ibrutinib is not expected to have systemic drug-drug interactions with P-gp substrates. However, it cannot be excluded that ibrutinib could inhibit intestinal P-gp and BCRP after a therapeutic dose. There are no clinical data available. To minimize the potential for an interaction in the gastrointestinal tract, narrow therapeutic range P-gp or BCRP substrates such as digoxin or methotrexate should be taken at least 6 hours before or after ibrutinib. Ibrutinib may also inhibit BCRP systemically and increase the exposure of drugs that undergo BCRP-mediated hepatic efflux, such as rosuvastatin.

Concomitant Use of Ibrutinib and Antiplatelet Agents and Anticoagulants

Warfarin or other vitamin K antagonists should not be administered concomitantly with ibrutinib. Use of ibrutinib in subjects requiring other anticoagulants or medications that inhibit platelet function may increase the risk of bleeding. Subjects with congenital bleeding diathesis have not been studied. Ibrutinib should be temporarily stopped at least 3 to 7 days pre- and post-surgery depending upon the type of surgery and the risk of bleeding.

Subjects requiring the initiation of therapeutic anticoagulation therapy (other than warfarin or a vitamin K antagonist) during the course of the study should be discussed with the sponsor's medical monitor.

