Due to the expected similarity among subjects in each cohort in pharmacokinetics, the rarity of the patient population, and expected tolerability of ibrutinib, a safety and pharmacokinetic run-in part (Part 1) will be conducted before starting the randomized part (Part 2) of the study. The safety and tolerability of the ibrutinib dose initially proposed based on modeling and simulation will be confirmed clinically during the run-in part (Part 1) of the study. The data generated during Part 1 will be used to confirm or adapt the dose prior to starting Part 2, by taking into account observed exposures in combination with the predicted exposures using the PBPK modeling. Interim pharmacokinetic and, if feasible, pharmacodynamic assessments will be conducted in order to monitor if predictions are correct (ie, ensure drug exposure is consistent with the equivalent adult dose of 560 mg). If exposure is within the approximate range observed in adult subjects treated at 560 mg/day adult steady-state exposure (median, 830 ng.h/mL; range, 250 to 1,500 ng.h/mL), then no dose adjustment will be required, provided there are no safety concerns. If exposure is not within the adult steady-state exposure range, then dose adjustments will be considered. A SET will review safety and pharmacokinetic data during the SET meetings (see Section 11.10). Safety will be assessed by evaluating the number of dose reductions and dose interruptions among the subjects treated in Part 1. Enrollment will begin with children in the 2 older age groups (6-11, 12-17 years) to assess pharmacokinetic and safety data before allowing enrollment of children in the youngest age group (1-5 years). The SET will meet to decide on any changes to the starting dose for each age group, and when enrollment may begin for the youngest age group. If dose adjustment requires a higher dose to be evaluated in the run-in part (Part 1), then the highest adult dose of 560 mg once daily will not be exceeded in children.

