4.3. Exposure Related Definitions

Treatment duration is the interval between date of first dose and end-of-treatment date. If date of end of treatment is not available, use last available treatment date.

Number of treatment cycles = the last cycle number - the first cycle number + 1.

The individual anticancer drugs that make up study treatment should be summarized separately. For the treatment phase, dosing information includes total dose received (the sum of actual dose administered), average dose level per administration (the ratio of total dose and treatment duration in cycles), and relative dose intensity:

$$\frac{\text{Sum of actual dose administered}}{\text{planned total cumulative dose for the regimen}}$$

Use the highest level of dose reduction to summarize categories - 'One dose reduction' and 'Two dose reductions'.

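### Attachment 4 gives one 75% ibrutinib reduction for strong and moderate CYP3A inhibitors; on its own interaction figures this fits the two moderate inhibitors but leaves a ketoconazole-like inhibitor at about 6 times usual AUC

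*Protocol*

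**What the plan says.** Attachment 4 of the protocol tells sites to avoid strong and moderate CYP3A inhibitors and then covers the case where one cannot be avoided. For strong inhibitors: "If the benefit outweighs the risk and a strong CYP3A inhibitor must be used, reduce the ibrutinib dose by 75" percent, with a temporary stop of 7 days or less as the alternative. For moderate inhibitors: "If a moderate CYP3A inhibitor must be used, reduce ibrutinib by 75" percent, for as long as the inhibitor is used. The reduced levels are the same for both classes: "rounded down to 80 mg/m² for starting dose of 329 mg/m² or to 110 mg/m² for dose of 440 mg/m²".

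The same paragraph supplies the interaction data. Ketoconazole, a strong inhibitor, raised dose-normalized Cmax and AUC "of ibrutinib by 29- and 24-fold, respectively" in 18 healthy subjects. Two moderate inhibitors, erythromycin and voriconazole, "increased AUC by 3.0-fold and 5.7-fold, respectively". It also cites safety data in 66 subjects (47 on moderate and 19 on strong inhibitors) without a meaningful rise in toxicity.

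Protocol Section 3.1 states the exposure that the pediatric dose is meant to match, the adult steady state at 560 mg/day: "median, 830 ng.h/mL; range, 250 to 1,500 ng.h/mL". Outside that range, dose adjustment is to be considered.

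**The concern.** A 75% cut exactly offsets a 4-fold interaction (1/0.25 = 4). That lies between the two moderate-inhibitor figures, 3.0 and 5.7, and far below the strong-inhibitor figure, 24. One instruction is therefore attached to two sets of data that differ several-fold, and the attachment does not say why one reduction serves both.

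At stake is the exposure of children and young adults on intensive chemoimmunotherapy who come to need a strong inhibitor during treatment. Major hemorrhage is the adverse event of special interest in this trial (Section 12.3.3). If the quoted interaction applied to them, the permitted reduced dose would give exposures well above those the trial set out to reproduce. A site reading Attachment 4 has no way to see this from the instruction alone.

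**Working it through.** **Inputs**
- Interaction, AUC: 24 (ketoconazole), 3.0 (erythromycin), 5.7 (voriconazole). Interaction, Cmax, ketoconazole: 29. All from Attachment 4.
- Adult AUC at 560 mg/day: median 830, range 250 to 1,500 ng.h/mL (Section 3.1).
- Dose-proportional pharmacokinetics (Section 1.3.2.1), so that residual exposure = interaction fold × fraction of dose remaining.

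**The plan's own figure.** 140/560 = 0.25, a 75% reduction. 140/1.7 = 82.4 mg/m², rounded down to 80. Then 80/329 = 0.243 (a 75.7% reduction) and 110/440 = 0.25. The stated 75% is reproduced.

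**Residual AUC**

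| Inhibitor | Fold | × 0.25 | × 80/329 | AUC from median 830 (ng.h/mL) |
|---|---|---|---|---|
| Erythromycin (moderate) | 3.0 | 0.75 | 0.73 | 622 / 605 |
| Voriconazole (moderate) | 5.7 | 1.43 | 1.39 | 1,183 / 1,150 |
| Ketoconazole (strong) | 24 | 6.0 | 5.8 | 4,980 / 4,844 |

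The last column gives the result at a fraction of 0.25, then at 80/329.

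**Against the range.** Both moderate medians lie inside 250 to 1,500. The ketoconazole median is 4,844/1,500 = 3.2 to 4,980/1,500 = 3.3 times the upper end. Even a subject who would otherwise sit at the bottom of the range comes to 250 × 5.84 = 1,459 up to 250 × 6.0 = 1,500. Residual Cmax with ketoconazole is 29 × 0.25 = 7.25 times usual (7.1 at 80/329).

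**Break-even.** The median stays at or below 1,500 if 830 × 0.25 × F ≤ 1,500, that is F ≤ 1,500/207.5 = 7.2. A strong inhibitor with an interaction of 7.2-fold or less would keep the median in range; ketoconazole, at 24, does not.

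**Rounding.** With the suspension doses in Attachment 1, the ketoconazole residual runs from 24 × 21/98 = 5.1 to 24 × 35/133 = 6.3 times for the step from 329 to 80 mg/m². For the step from 440 to 110 mg/m² it runs from 24 × 63/266 = 5.7 to 24 × 196/560 = 8.4 times. The 8.4 arises at the largest body surface areas, because the 440 table is capped at 560 mg and the 110 table is not. Rounding does not change the picture.

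**The case against.** Several points limit this, and most of them stand in part.

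- **Few subjects should be affected.** Ongoing strong-inhibitor treatment is an exclusion (Section 4.2, criterion 1). Attachment 4 says to avoid such drugs and to monitor closely. Sections 8.1 and 8.1.2 steer antifungal prophylaxis for subjects on ibrutinib away from azoles. Enrollment has ceased, although Section 17.9.1 lets ongoing patients continue treatment. This lowers the number at risk but leaves the instruction unexplained for those to whom it applies.
- **Treatment can be stopped instead.** A stopped subject does not reach 6-fold. The option is limited to 7 days or less, so for a longer inhibitor course the sentence leaves only the reduction.
- **There are supporting safety data.** Nineteen subjects on strong inhibitors are cited without a meaningful increase in toxicity, but neither their ibrutinib dose nor their exposure is given. Section 1.3.2.1 reports no meaningful relation of bleeding or infection to exposure; the documents do not show that this analysis reached values near 5,000 ng.h/mL. Section 1.3.2.2 reports no dose-limiting toxicity up to 840 mg with RICE in adults. That is 840/560 = 1.5 times the reference dose, against a residual of about 6 here.

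A reader might also infer more than the documents support:

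- **That every strong inhibitor leaves exposure 6 times high.** The 24-fold figure is for ketoconazole alone in 18 healthy adults. No figure is given for the other strong inhibitors in Attachment 5.
- **That the instruction and the exposure range cannot both be met.** Section 3.1 uses the range to confirm the dose in Part 1. It is not stated as a ceiling for co-medication, and treatment can be stopped. This is an unexplained mismatch, not a strict contradiction.
- **That the SAP counts these subjects' adverse events as occurring at a quarter of the dose.** No SAP table reports adverse events by ibrutinib dose. SAP Section 6.1.1 splits treatment-emergent events by any and by strong CYP3A inhibitor use, and Section 4.4 summarizes reasons for dose modification. Relative dose intensity in Section 4.3 measures dose, and the SAP does not read it as exposure.

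**Conclusion.** The point holds as a mismatch within Attachment 4 and against the exposure range in Section 3.1. The common 75% reduction brings median AUC with the two moderate inhibitors to 0.75 to 1.43 times usual. With the only strong inhibitor for which a figure is quoted, it leaves about 5.8 to 6.0 times usual.

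This rests on four assumptions: dose-proportional pharmacokinetics; transfer of the adult fold-changes to the trial's subjects; an inhibitor about as strong as ketoconazole; and an unperturbed exposure near the adult median. The third matters most, since below about 7.2-fold the median stays in range. The documents do not show that exposure at this level is harmful, and they do not say how many subjects would receive a strong inhibitor. The matter is worth correcting because it bears on patient safety, costs little, and the support offered gives neither dose nor exposure.

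**What to change.** The sponsor should reconcile the strong-inhibitor instruction in Attachment 4 with the 24-fold figure in the same paragraph and with the exposure range in Section 3.1. Otherwise it should state the data that justify one reduction for both classes, including the ibrutinib dose and exposure of the 19 subjects on strong inhibitors. Which dose or clinical rule applies is for the sponsor to settle; none is proposed here.

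The cost is a revision of the attachment's wording, or a short added justification. No change to the SAP is needed on this point.
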